7 STUDY TREATMENT(S)

7.1 Description of investigational medicinal product(s)

The IMPs used in this study are bimekizumab, adalimumab, and placebo.

- Bimekizumab will be supplied in a 1mL prefilled syringe (PFS) at a concentration of [REDACTED] for sc injection.
- Adalimumab is commercially available and will be supplied as a PFS for sc injection (at a concentration of 40mg/0.8mL or 40mg/0.4mL depending on regional availability) in a single-use syringe.
- Placebo will be supplied as 0.9% sodium chloride aqueous solution (physiological saline, preservative-free) of pharmacopoeia (USP/Ph.Eur) quality in a 1mL PFS for sc injection.

Further details of the IMPs and their specifications are provided in the IMP Handling Manual.

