2.2.1.3 Other efficacy variables

Change from Baseline variables evaluated are relative to the Baseline (first dose) Visit. In addition, for subjects who start with adalimumab and switch treatment at the Week 24 Visit, change from Baseline variables during the bimekizumab treatment period will be evaluated relative to both the Baseline (first dose) Visit and the Week 24 Visit.

For simplicity, "change from Baseline" is used below for all such variables. Greater detail on the definition of Baseline for different summaries is provided in the Section 3.2. Unless otherwise stated, PASI responder rates will be calculated relative to the Baseline (first dose) Visit.

The other efficacy variables are:

- PASI50, PASI75, PASI90, and PASI100 response
- Time to PASI50, PASI75, PASI90, and PASI100 response during the Initial Treatment Period
- Absolute and percent change from Baseline in PASI score
- Percent of subjects with absolute PASI score ≤ 1 , ≤ 2 , ≤ 3 and ≤ 5
- IGA response (Clear with at least a 2-category improvement relative to Baseline)
- IGA response (Clear or Almost Clear with at least a 2-category improvement relative to Baseline)
- Shift from Baseline in IGA score
- Absolute and percent change from Baseline in the BSA affected by PSO
- Percent of subjects with absolute BSA=0%, $\leq 1\%$, $\leq 3\%$ and $\leq 5\%$
- Absolute and percent change from Baseline in the product of IGA and BSA (IGAxBSA)
- Change from Baseline in the Dermatology Life Quality Index (DLQI)
- Percent of subjects achieving a DLQI total score of 0 or 1
- Percentage of subjects achieving a minimal clinically important difference (MCID) (improvement from Baseline of 4 or more) in the DLQI
- Change from Baseline in Patient's Global Assessment of Disease Activity (PGADA) for the arthritis visual analog scale (VAS) in subjects with PsA as defined by PASE score at Baseline
- Change from Baseline in Patient Global Assessment of PSO score
- Change from Baseline in the Patient Symptom Diary scores
- Patient Symptom Diary response rates
- Scalp-specific Investigator's Global Assessment (scalp IGA) response (Clear or Almost Clear with at least a 2-category improvement relative to Baseline) for subjects with scalp PSO at Baseline
- Change from Baseline in modified Nail Psoriasis Severity Index (mNAPSI) score for subjects with nail PSO at Baseline

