3.2 Definition of Baseline values

A Baseline value for a subject is defined as the latest measurement for that subject up to and including the day of administration of first study medication, unless otherwise stated. If a Baseline assessment is taken on the same day as first administration of study medication, it is eligible to be used as the Baseline value, even in the case that the time of the assessment is recorded as taking place after the time of first study medication administration. This is considered acceptable as this measurement is still the best representation of the Baseline value of the given assessment since it is highly unlikely that the study medication could have an impact on any measurement in such a short period of time. However, such cases should be rare as study center personnel are instructed to do all assessments at the Baseline visit prior to administering study medication. One exception to this rule is plasma concentration. If Baseline plasma concentration is measured at a time after the first administration of study medication, then it should not be eligible to be considered as a Baseline plasma concentration. Such cases should be discussed with the quantitative clinical pharmacologist. If a Baseline measurement is missing or not collected, and a Screening value is available, the Screening value will be utilized as Baseline instead.

For subjects who start with adalimumab and switch treatment at the Week 24 Visit, an additional bimekizumab Baseline defined as the measurement at Week 24 will be used. If a Week 24 Visit measurement is missing, baseline will be the latest measurement prior to the first dose of bimekizumab. The variables listed below will also be summarized based on bimekizumab Baseline:

- PASI score

- DLQI
- Laboratory data (only in shift tables)

Note that for any laboratory value that occurs on the day of treatment switch, that lab value will be attributed and summarized for the treatment they were on previously. For subjects that switch from Adalimumab to Bimekizumab, the Baseline value is the laboratory value of the day of treatment switch.

Baseline values for component scores should be computed using components from the same visit where the relevant measurements were recorded prior to dosing. For example, if the Screening visit has all of the components, but the Baseline visit is missing one or more components, the Baseline value for the component score should be calculated using the Screening visit values.

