For laboratory shift tables through initial and maintenance treatment period, the treatment groups BKZ 320mg Q4W, BKZ 320mg Q4W/Q8W, ADA/ BKZ 320 mg Q4W and BKZ Total will be presented. For subjects randomized to ADA, only data after the switch to Bimekizumab will be considered. The last value prior to the switch will be considered as baseline.

A by-subject listing of all laboratory data will be provided. This listing will be presented by treatment group and will include: center, subject identifier, age, sex, race, weight, visit, laboratory variable, result (with abnormal values flagged as “L” or “H” accordingly) and unit.

Markedly abnormal values are defined as those with a severity of Grade 3 and above based on the common terminology criteria for adverse events (CTCAE) criteria (U.S. Department of Health and Human Services 2010). Definitions of markedly abnormal values using the Grade 3 cut points are given in the tables below for age ranges of ≥ 17 years (Table 10–1 for markedly abnormal biochemistry values and Table 10–2 for markedly abnormal hematology values).

Tables summarizing markedly abnormal values should include a summary (counts and percentages) of markedly abnormal labs observed at any time while on treatment (ie, treatment-emergent markedly abnormal [TEMA]). For this summary, Baseline values and values observed more than 140 days after the last administration of study medication are not considered. The laboratory results classified as Grade 3 or Grade 4 will be summarized and listed separately.

Summaries in the ADA/BKZ arm will be provided to examine markedly abnormal labs occurring within 70 days and >70 days of the treatment switch. The time since the treatment switch is calculated as the number of days since the final dose of adalimumab. Only lab values recorded after the start of bimekizumab treatment will be included. 70 days was chosen as it is approximately equal to five half lives of adalimumab.

Table 10–1: Definitions of Markedly Abnormal Biochemistry Values

Parameter name	Conventional		Standard		Abnormal Designation
	Unit	Criteria	Unit	Criteria	
Creatinine	mg/dL	>3.0 x ULN	mmol/L	>3.0 x ULN	AH
Glucose	mg/dL	<40 >250	mmol/L	<1.7 >13.9	AL AH
Calcium	mg/dL	>12.5 <7.0	mmol/L	>3.1 <1.75	AH AL
Magnesium	mg/dL	>3.0 <0.9	mmol/L	>1.23 <0.4	AH AL
Potassium	mmol/L	>6.0 <3.0	mmol/L	>6.0 <3.0	AH AL
Sodium	mmol/L	>155 <130	mmol/L	>155 <130	AH AL

Table 10–2: Definitions of Markedly Abnormal Hematology Values

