10.4 Vital signs, physical findings, and other observations related to safety

10.4.1 Vital signs

The following vital signs variables should be summarized: systolic blood pressure (mmHg), diastolic blood pressure (mmHg), body temperature (°C) and heart rate (beats/min). The following summary will be provided:

- A summary of the absolute and change from Baseline value for each vital sign variable by treatment group and visit through initial and maintenance treatment period for the SS
- A summary of the number and percentage of subjects experiencing at least one markedly abnormal value for a vital sign variable as defined in Table 10–3, by treatment group, through Week 24 for the SS and through initial and maintenance treatment period for the BKZ set

Table 10–3: Definitions of Markedly Abnormal Blood Pressure Values

Parameter (unit)	Markedly Abnormal Low	Markedly Abnormal High
Systolic blood pressure (mmHg)	<90 and a decrease from Baseline of \geq 20	>180 and an increase from Baseline of \geq 20
Diastolic blood pressure (mmHg)	<50 and a decrease from Baseline of \geq 15	>105 and an increase from Baseline of \geq 15

A by-subject listing of all vital signs data should be provided. This listing should be presented by treatment group and will include: center, subject identifier, age, sex, race, weight, visit, vital sign variable and result (with abnormal values flagged as “L” or “H” accordingly).

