10.4.5 Patient Health Questionnaire 9 (PHQ-9)

The PHQ-9 is a multipurpose instrument for screening, diagnosing, monitoring, and measuring the severity of depression. The PHQ-9 scores for depression range from 0 to 27 with higher scores indicating worse state. A score of 5-9 is considered to be minimal symptoms of depression. If any of the 9 questions are missing, then the score is treated as missing. A score of 10 to 14 is considered minor depression, dysthymia, or mild major depression. A score of 15 to 19 is considered to indicate moderately severe major depression, and a score ≥ 20 is considered to be severe major depression.

MI-MCMC/monotone regression method will be used to impute missing data. If the imputation model cannot converge, last observation carried forward (LOCF) will be used.

Change from Baseline in PHQ-9 is derived as post-Baseline score minus Baseline score. It will be summarized by treatment group through initial and maintenance treatment period for the SS and for the BKZ Week 24 Set for subjects switching from adalimumab to bimekizumab.

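### For subjects who switch from adalimumab to bimekizumab, the change part of the blood-pressure abnormality rule, and PHQ-9 change, are referenced to a value taken before adalimumab

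*SAP*

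**What the plan says.** The default Baseline in SAP 3.2 is "the latest measurement for that subject up to and including the day of administration of first study medication". Protocol 7.1 states: "The IMPs used in this study are bimekizumab, adalimumab, and placebo". For a subject randomized to adalimumab, Baseline is therefore the Week 0 value (or Screening, if Week 0 is missing), taken before adalimumab.

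For switchers, SAP 3.2 provides that "an additional bimekizumab Baseline defined as the measurement at Week 24 will be used", falling back to the last measurement before the first bimekizumab dose if Week 24 is missing. It continues: "The variables listed below will also be summarized based on bimekizumab Baseline". Three items follow: PASI score, DLQI, and laboratory data in shift tables only. PHQ-9 and vital signs are absent.

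Two analyses then use Baseline without further qualification:

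- **SAP 10.4.1, Table 10-3.** Markedly abnormal blood pressure is tabulated "through Week 24 for the SS and through initial and maintenance treatment period for the BKZ set". Each limit has two parts. Systolic must be above 180 with a rise of at least 20, or below 90 with a fall of at least 20. Diastolic must be above 105 with a rise of at least 15, or below 50 with a fall of at least 15.
- **SAP 10.4.5.** PHQ-9 change from Baseline is summarized for the SS and also "for the BKZ Week 24 Set for subjects switching from adalimumab to bimekizumab".

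By contrast, SAP 10.3 says of switchers in the laboratory shift tables over the same period: "The last value prior to the switch will be considered as baseline".

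**The concern.** Both summaries are meant to describe what happens on bimekizumab. Under SAP 3.6, data from the adalimumab arm after Week 24 enter the BKZ Q4W column of the BKZ Set safety tables. The PHQ-9 summary in the BKZ Week 24 Set is planned specifically for switchers. A reference value some 24 weeks and a full adalimumab course earlier mixes change on adalimumab with change on bimekizumab.

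For blood pressure this can alter which subjects are counted. For PHQ-9 it means the reported spread describes change since before adalimumab, not change since the switch. Protocol 14.5.1 singles out the safety of this switch for additional summaries, and Protocol 12.1.1.4 lists depression among the prespecified safety topics.

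**Working it through.** The plan gives no figure to reproduce. The check is a trace of definitions followed by arithmetic on assumed values.

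**1. Is a pre-bimekizumab value available?** Yes. Protocol 7.2 puts the adalimumab arm's first bimekizumab dose at Week 24. Protocol 8.3.4 lists vital signs and PHQ-9 among the Week 24 procedures done before dosing.

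**2. When does the choice of baseline change a blood-pressure count?** Let B0 be the Week 0 value, B24 the Week 24 value and X a systolic reading on bimekizumab with X > 180. The reading is counted if X − B ≥ 20, that is, if B ≤ X − 20. The two baselines disagree only when exactly one of B0 and B24 is at or below X − 20. If X ≤ 180, the high limit is not met and the baseline is irrelevant. The low limit and the diastolic limits work the same way.

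Take X = 182, so X − 20 = 162. The readings below are assumed, not trial data.

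| B0 | B24 | X | Change from Week 0 | Counted? | Change from Week 24 | Counted? |
|---|---|---|---|---|---|---|
| 160 | 178 | 182 | 182 − 160 = +22 | yes | 182 − 178 = +4 | no |
| 170 | 150 | 182 | 182 − 170 = +12 | no | 182 − 150 = +32 | yes |

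The error can go either way.

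**3. How many subjects?** The adalimumab arm is planned at about 150 of 450, or 150/450 = one third. That is a ceiling. An affected subject must reach the switch, cross an absolute limit on bimekizumab, and have B0 and B24 on opposite sides of the change threshold. The documents give no rate for this.

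**4. What is recoverable for PHQ-9?** Let P0, P24 and Pt be the scores at Week 0, at Week 24 and at a later visit. For each subject, Pt − P24 = (Pt − P0) − (P24 − P0). Averaged over the same subjects, the mean change since the switch is the difference between two reported means. An assumed subject with scores 9, 4 and 8 shows 4 − 9 = −5 at Week 24 and 8 − 9 = −1 later. The difference, −1 − (−5) = +4, is the change since the switch.

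The spread cannot be recovered this way. Var(Pt − P24) = Var(Pt − P0) + Var(P24 − P0) − 2·Cov(Pt − P0, P24 − P0), and a by-visit table does not report the covariance. The median and extremes cannot be recovered either.

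**The case against.** The strongest reply is that this is a considered choice with little consequence. SAP 13.1 (Amendment 1) records that PHQ-9 was taken off the list of variables given a Week 24 baseline. The Week 0 value is free of study drug and common to all the arms pooled under BKZ Total. Switch safety is assessed mainly elsewhere: adverse events starting after the first bimekizumab dose and split at 70 days (10.2.1, 10.2.2), markedly abnormal laboratory values split the same way (10.3), adjudicated suicidality events (10.2.3.5) and the eC-SSRS (10.4.4.2). All vital signs are listed by subject.

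Much of this stands. It supports keeping the Week 0 summary and treating the matter as descriptive. It does not settle the point. The amendment record shows intent for PHQ-9 but gives no reason, names vital signs nowhere among the removed or retained items, and introduces the PHQ-9 summary for switchers in the same amendment. Listings do not correct counts in a summary table. The laboratory precedent covers shift tables only, but it applies the same principle to the same subjects over the same period.

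Two stronger readings are tempting and not supported:

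- A reader might infer that PHQ-9 deterioration after the switch is hidden. SAP 10.4.5 summarizes PHQ-9 across both treatment periods against one reference, and the imputation rule for the BKZ Week 24 Set (4.2.1.6) covers visits from Baseline to Week 56. The mean course before and after the switch is therefore visible.
- A reader might infer that the SAP already promises both baselines, because 2.2.1.3 says change variables for switchers "will be evaluated relative to both the Baseline (first dose) Visit and the Week 24 Visit". That sentence concerns efficacy variables and defers to 3.2. SAP 3.10 classes PHQ-9 as safety, and blood pressure was never an efficacy variable.

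**Conclusion.** The point holds for blood pressure and, in a narrower sense, for PHQ-9. In the BKZ Set table, the change part of Table 10-3 uses a pre-adalimumab reference for switchers, so a switcher who crosses an absolute limit on bimekizumab can be wrongly counted or missed. For PHQ-9, the mean change since the switch can be derived, but its SD and distribution are not reported.

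A reader might take about 150 subjects as the number of altered results. It is the planned arm size and only an upper bound. The true number is unknown and depends on how many switchers cross an absolute limit.

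The conclusion rests on two assumptions. The first is that the SAP 3.2 list is exhaustive, which follows from the default definition and the wording that introduces the list; no sentence names the baseline for either measure outright. The second is that the switchers' PHQ-9 table shows Week 24 as well as later visits. SAP 3.6 limits the display to Weeks 28 to 56 only for PASI scores and DLQI. The co-primary analyses, the testing sequence and Type I error control are untouched.

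**What to change.** For subjects randomized to adalimumab, add two items to the bimekizumab-Baseline list in SAP 3.2: vital signs (Table 10-3, BKZ Set) and PHQ-9 (BKZ Week 24 Set). Use the Week 24 pre-dose value or, if it is missing, the last value before the first bimekizumab dose. Refer to this baseline explicitly in 10.4.1 and 10.4.5, and keep the Week 0 version alongside.

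The derivation and its missing-value fallback already exist in SAP 3.2, and the principle is already applied to laboratory shift tables in 10.3. The cost is a change of wording, reuse of existing programming and one extra set of descriptive columns.

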
3.3 Mapping of data from early withdrawal visits

If the early withdrawal visit occurs at a scheduled visit as outlined in the schedule of assessments, then no mapping is necessary, and any early withdrawal assessments should correspond to that scheduled visit. Premature study withdrawal visit assessments that occur on a date after a scheduled visit will be assigned to the next scheduled site visit per the protocol following the last visit where assessments were available. This approach means that there is a chance that data will be mapped to a visit where a given assessment was not actually collected per the protocol schedule of assessments. Such data would not be summarized in by-visit tables (though it would be available in the listings).

The only exception to the above rule is for anti-bimekizumab antibody assessments, in which all early withdrawal visit assessments will be assigned to the next scheduled visit at which anti-bimekizumab antibody are assessed. All by-visit summaries will contain nominal visits only. Unscheduled visits will not be mapped to scheduled visits. Note that based on the early withdrawal mapping conventions described above, a mapped early withdrawal visit is considered as observed at that visit and should be summarized as such in the tables.

3.4 Protocol deviations

Important protocol deviations are deviations from the protocol which potentially could have a meaningful impact on study conduct or on the primary efficacy, key safety, or PK outcomes for an individual subject. The criteria for identifying important protocol deviations will be defined within the appropriate protocol-specific document at study start. Important protocol deviations will be reviewed as part of the ongoing data cleaning process. Important protocol deviations including those that lead to exclusion from the analysis sets will be identified and documented prior to unblinding.

3.5 Analysis sets

For all analysis sets, each unique subject is only counted once, even if the same subject has more than one unique subject identification.

3.5.1 Enrolled Set

The Enrolled Set (ES) will consist of all subjects who have given informed consent.

3.5.2 Randomized Set

The Randomized Set (RS) will consist of all randomized subjects.

3.5.3 Safety Set

The Safety Set (SS) will consist of all subjects that received at least 1 dose of the IMP.

3.5.4 Full Analysis Set

The Full Analysis Set (FAS) will consist of all randomized subjects that receive at least 1 dose of the IMP and have a valid measurement of each of the co-primary efficacy variables at Baseline.

3.5.5 Bimekizumab Set

The Bimekizumab Set (BKZ Set) will consist of all subjects who have received at least 1 dose of bimekizumab in this study.

3.5.6 Bimekizumab Week 24 Set

The BKZ Week 24 Set will consist of all subjects who have received at least 1 dose of BKZ on or after Week 24.

3.5.7 Maintenance Set

The Maintenance Set (MS) will consist of all subjects who have received at least 1 dose of active IMP (bimekizumab or adalimumab) in the Maintenance Treatment Period (at Week 16 or later).

3.5.8 Per Protocol Set

The Per-Protocol Set (PPS) will consist of all subjects in the RS who had no important protocol deviations affecting the primary efficacy variables. Important protocol deviations will be pre-defined and subjects with important protocol deviations will be evaluated during ongoing data cleaning meetings prior to unblinding of the data.

3.5.9 Pharmacokinetics Per-Protocol Set

The Pharmacokinetics Per-Protocol Set (PK-PPS) will consist of all randomized subjects who received at least 1 dose of the IMP and provided at least 1 quantifiable plasma concentration post-dose without important protocol deviations that would affect the concentration.

3.6 Treatment assignment and treatment groups

It is expected that subjects receive treatment as randomized and hence safety analyses will be based on the SS, as randomized. However, if after unblinding it is determined that subjects randomized to a treatment arm had never received such treatment, then for safety analyses, these subjects will be reallocated to the appropriate received treatment groups, unless otherwise specified.

Efficacy analyses should be performed according to randomized treatment and not actual treatment received.

Summaries based on SS or RS will be provided by “BKZ 320mg Q4W”, “BKZ 320mg Q4W/Q8W”, “BKZ Total” and “ADA” treatment groups. The ADA group will only be presented from Baseline to Week 24 in the by-visit summaries.

Summaries based on BKZ Week 24 set will be provided by “BKZ 320mg Q4W”, “BKZ 320mg Q4W/Q8W” and “ADA/BKZ 320mg Q4W” treatment groups for disposition, baseline assessments and efficacy. The ADA/BKZ 320mg Q4W group will be presented from Week 28 to Week 56 in the by-visit summaries for the PASI scores and the DLQI only.

For safety, summaries on the BKZ set will be provided by “BKZ 320mg Q4W”, “BKZ 320mg Q8W” and “BKZ Total”. BKZ Q4W will include data from subjects in the BKZ Q4W/Q8W arm (up to Week 16) and the ADA/BKZ Q4W arm (after Week 24).

Safety summaries on the BKZ Week 24 set will be provided for subjects switching from Adalimumab to Bimekizumab.

Summaries based on the Maintenance set will be provided by “BZK 320mg Q4W”, “BKZ 320mg Q4W/Q8W” and “BKZ Total”.

